9.3.3. Endometrial Biopsy

The protocol-specified endometrial biopsy procedure was performed at Baseline for all patients in MVT-601-3101 and MVT-601-3102, and at the pivotal phase 3 study Week 24/ET visit for all patients who participated in MVT-601-3101 only. Starting from protocol amendment 2.0, endometrial biopsy procedure was required for all patients in the extension study at Week 52 and Early Termination Visit (except for patients whose last dose of study drug was taken during Week 32 or earlier or within four weeks after completion of the Week 52 endometrial biopsy). However, the procedure may have been done if it would aid in the evaluation of an ongoing adverse event. An endometrial biopsy at Week 104 was recommended for all patients who complete the open-label extension; however, patients have the option to opt out. Consensus readings by independent pathologists were performed on all endometrial biopsies.

The Week 52, Week 104, and Early Termination endometrial biopsy samples will be submitted to the central laboratory. If the Week 52, Week 104, or Early Termination biopsy specimen is inadequate, a transvaginal ultrasound for endometrial thickness should be obtained and read locally. The transvaginal ultrasound findings will be used to determine if further action is required. No further action is required for endometrial thickness ≤ 5 mm. Repeat endometrial sampling will be collected for endometrial thickness > 5 mm at any location or any other endometrial abnormality is present. Unscheduled endometrial biopsies may also be performed when medically indicated and as deemed necessary by the investigator.

Endometrial biopsies will be summarized using frequencies and percentages according to primary diagnosis and secondary diagnosis from the consensus reading (Table 23). Primary and secondary diagnosis from consensus reading evaluation are summarized Table 23. Endometrial biopsies performed in the pivotal phase 3 studies and extension study will be summarized by pivotal phase 3 study treatment group and by visit. Any repeat endometrial biopsies performed will also be summarized. Biopsy reported in the pivotal study CSRs will be excluded from the extension study analyses. All endometrial biopsy findings and transvaginal ultrasound data will also be provided in a by-patient listing, including visits in both the pivotal phase 3 study and extension study.

Table 23: Categories of Primary Diagnosis in Endometrial Biopsies

Primary Diagnosis Category	Secondary Diagnosis
Normal-Proliferative	
 • Weakly proliferative • Proliferative • Disordered proliferative
Normal-Secretory/Menstrual/Mixed	
 • Secretory • Menstrual • Progesterational/Decidualized • Mixed
Normal-Atrophic/Indeterminate/Inactive	
 • Atrophic • Indeterminate/Inactive

Hyperplasia	
 • Simple hyperplasia without atypia • Simple hyperplasia with atypia • Complex hyperplasia without atypia • Complex hyperplasia with atypia
Carcinoma	–
Inadequate	–
Missing	–
Additional Diagnosis (Other reported findings)	
 • Reactive/Inflammatory • Polyp • Metaplasia • Glandular and/or Stromal Breakdown

9.3.4. Mammogram

A requirement for post-treatment mammograms was added starting with protocol amendment 3.0 as follows: For women who are or become ≥ 40 years old at the time of the visit, the protocol-specified local mammogram was to be performed at Week 52 or at Week 104/Early Termination. If a patient had a recent mammogram per standard of care within the six months before Week 52 that was Breast Imaging Reporting and Data System category 1 or 2 or equivalent or had benign findings, as determined by the investigator or medical monitor, a mammogram is not required at Week 52 but should be completed by Week 104/Early Termination. If a patient turns 40 years old after the Week 52 visit has occurred, a mammogram should be performed no later than the Week 104/Early Termination visit. All mammogram results will be read locally using Breast Imaging Reporting and Data System categories or equivalent and recorded in the eCRF.

Mammograms performed in the extension study at Week 52, Week 104//Early Termination will be summarized. Number and percentage of patients in each Breast Imaging Reporting and Data System category or equivalent will be summarized by visit and by pivotal phase 3 study treatment group. Mammogram data will also be provided in a by-patient listing in the extension study.

9.3.5. Bone Mineral Density

Corrected BMD data as determined by the central radiology laboratory in the three prespecified anatomical locations will be used for analysis: lumbar spine (L1–L4), total hip, and femoral neck.

BMD measured at Baseline and post-baseline visits will be summarized descriptively by pivotal phase 3 study treatment group and each measured anatomical location for all patients in the Extension Safety population. Mean change and percentage changes from baseline along with 95% CIs will be summarized by pivotal phase 3 study treatment group, visit and anatomical location. Percentage change from baseline with its corresponding 95% CI will be plotted by

visit, pivotal phase 3 study treatment group, and anatomical location. Percentage change from Week 12 to subsequent visits along with 95% CIs will be summarized by pivotal phase 3 study treatment group, visit and anatomical location.

A mixed-effects model with repeated measures will be used to assess BMD at each visit. The model will have age at Baseline, treatment, visit, treatment-by-visit interaction, Baseline BMD value, stratification factors (geographic region and time since initial surgical diagnosis), body mass index at baseline, race (Black/African American versus Other) as fixed effects using an unstructured variance-covariance matrix. If the mixed-effects model fails to converge, a first-order autoregressive variance-covariance matrix will be used. Here treatment refers to pivotal phase 3 study treatment group. Least squares mean on each anatomical location will be presented and plotted by pivotal phase 3 study treatment group at each visit with associated 95% CIs. Specifically for percentage change from Week 12 to subsequent visits, week 12 BMD value is considered as a baseline.

Categorical representation of percentage change from Baseline to post-baseline visits will be presented by the number and proportion of patients who had BMD increased ($> 0\%$), no change ($= 0\%$) and decreased by $< 2\%$, $\geq 2\%$ to 3% , $> 3\%$ to 5% , $> 5\%$ to 8% , and $> 8\%$ by pivotal phase 3 study treatment group and anatomical location. The 95% CIs will be provided for the respective proportions. The number and percentage of patients meeting a bone mineral density decrease of at least 4% , 5% , 6% , 7% , or 8% by anatomical location (lumbar spine, total hip, or femoral neck) will be estimated with 95% CIs by the pivotal phase 3 study treatment group.

Categorical changes from Baseline in overall BMD (defined as lumbar spine and total hip) also will be assessed at post-baseline visits. Femoral neck evaluates a smaller area of bone mass than the total hip and is prone to lower precision in the measurement (Leslie 2007; ISCD Official Positions 2015). Since femoral neck BMD may be associated with discordant readings compared with the total hip or lumbar spine due to technical considerations, it is not expected to add meaningful interpretation of overall BMD changes in response to treatment, though will be included for completeness.

Z-scores will be summarized by pivotal phase 3 study treatment group, visit, and anatomical location with descriptive statistics including 95% CIs. Number and percentage of patients with a Z -score < -2.0 will be presented by pivotal phase 3 study treatment group, visit, and anatomical location. Number and percentage of patients with a Z score- change from baseline ≥ 0 , < 0 to -0.25 , < -0.25 to -0.5 , < -0.5 to -0.75 , < -0.75 to -1.0 , < -1.0 to -2.0 and < -2.0 will be presented by pivotal phase 3 study treatment group and anatomical location at Week 24, Week 52 and Week 104.

BMD change from baseline in the category of decreased, no change, and increased will be presented by pivotal phase 3 study treatment group, visit, and anatomical location.

BMD percentage changes from Baseline will also be summarized by intrinsic factors (eg, age, race, body mass index) and extrinsic factors (eg, geographic region). Subgroups will include, but will not be limited to, the subgroups outlined in Table 24.

Table 24: Planned Subgroup Analyses

Subgroup Name	Subgroup Level
---------------	----------------

Geographic region	North America, Rest of World
Age category (years)	< 35, ≥ 35
Race	Black or African American, Other
Ethnicity	Hispanic or Latino, Not Hispanic or Latino
BMI (kg/m ²) at Baseline	< 25, ≥ 25

Abbreviations: BMI = body mass index. For patients reporting multiple races, those who reported “Black/African-American” as one of the races will be included in the “Black or African-American” category.

Post-treatment BMD

Determination of bone mineral density by DXA at post-treatment follow-up of findings will proceed according to the rules defined by original protocol or amendments. Complete data collected during the post-treatment Follow-Up period will be summarized and reported in an addendum to the final clinical study report.

Patients required to have post-treatment follow up for BMD are defined according to the rules defined in [section 2.1](#) (Table 2):

All available 6-month and 12-month post-treatment follow-up BMD data will be summarized to display the number and percent of patients who completed post-treatment follow-up, who met the threshold for recovery, and who did not meet the threshold for recovery. Summary statistics will be provided for post-treatment DXA by anatomic location at 6 months and 12-months. Summary of BMD loss recovery during post treatment follow up will be provided by location and by pivotal phase 3 study treatment group. Summaries will be presented of percent change in BMD from baseline for patients who entered post-treatment follow-up period by anatomic location and by pivotal phase 3 study treatment group. For patients who decline to participate in the 6-month and 12-month PTFU, reasons of decline will be summarized in the by-patient listing.

Post-treatment follow-up medical and gynecological history, concomitant medications, and bone fracture events will be listed in the by-patient listing.

For patients with PTFU scans showing a bone loss of $\geq 3\%$ at the lumbar spine and/or total hip at the 6-month and 12-month PTFU visit compared with the pivotal study baseline, clinical laboratory evaluations including vitamin D, thyroid-stimulating hormone, parathyroid hormone, creatinine, calcium, and phosphorous will be listed in the by-patient listings.

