AM 3.1	
At the Week 36, Week 52, and Week 104 visits, DXA is required.
 
 • For Early Termination occurring before Week 36, DXA is not required at the Early Termination visit unless it will aid in the assessment of an adverse event or if the most recent DXA bone mineral density loss at lumbar spine (L1-L4) or total hip was > 2% relative to the pivotal phase 3 study baseline. • For Early Termination occurring at or after the Week 36 visit, DXA is required at Early Termination unless a DXA result is available from within six weeks prior to Early Termination. 	
Post-Treatment DXA is required at 6 months (± 1 month):
 
 • For Early Termination occurring before Week 36: 
 – the most recent DXA bone mineral density loss at lumbar spine (L1-L4) or total hip was > 2% relative to the pivotal phase 3 study baseline. • For Early Termination occurring at or after the Week 36 visit: 
 – the most recent DXA scan was at Week 24 and on the most recent DXA scan, bone mineral density loss at the lumbar spine (L1-L4) or total hip was > 2%, relative to the pivotal phase 3 study baseline. – the most recent DXA was after the Week 24 visit and on the most recent DXA scan, bone mineral density loss at the lumbar spine (L1-L4) or total hip was > 3%, relative to the pivotal phase 3 study baseline. • For patients who complete the open-label extension study: 
 – at the Week 104 visit or on the most recent DXA scan, bone mineral density loss at the lumbar spine (L1-L4) or total hip was > 3%, relative to the pivotal phase 3 study baseline. 
12-Month Post-Treatment DXA: patients have 6-month post-treatment follow-up scans that show bone loss of > 1.5% at the lumbar spine and/or > 2.5% at total hip compared with the pivotal phase 3 study baseline, patients are strongly encouraged to come back to the clinic for an additional post-treatment follow

[figure not shown]

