
AM 4.0
	
 • For Early Termination occurring before Week 36, DXA is not required at the Early Termination visit unless it will aid in the assessment of an adverse event or if the most recent DXA BMD loss at lumbar spine (L1-L4) or total hip was > 2% relative to the parent study baseline. • For Early Termination occurring at or after Week 36, DXA is required at Early Termination unless a DXA result is available from within six weeks prior to Early Termination. 	
6-month and 12-Month Post-Treatment DXA:
 
 • All ongoing patients, after they complete the Week 104 visit or terminate the study early, will return for a 6-month PTFU DXA and a 12-month PTFU DXA • All patients who completed treatment or terminated from the study early and are within 6 months from their last day on treatment will be requested to return for a 6month PTFU DXA and again for a 12-month PTFU DXA. • All patients who completed treatment or terminated from the study early and are past 6 months but within 12 months from their last day on treatment will be requested to return for a 12-month post-treatment DXA. • For patients who are outside the PTFU visit windows, PTFU DXA is still recommended. However, if the patient is beyond 14 months from last day on treatment, she does not need to return for 12-month post-treatment DXA. 
If patients have 6-month or 12-month PTFU scans that show bone loss of $\geq 3\%$ at the lumbar spine and/or total hip compared with the parent study baseline, patients should be referred to and strongly encouraged to see a bone specialist for further evaluation of the bone loss.

---------------	--	---

The 6-month and 12-month PTFU visits will also measure post-treatment medical and gynecological history, concomitant medications, and bone fracture events. Patients should also have the following clinical laboratory evaluations: vitamin D, thyroid-stimulating hormone, parathyroid hormone, creatinine, calcium, and phosphorous at the 6-month and 12-month PTFU visit only if PTFU scans show a bone loss of $\geq 3\%$ at the lumbar spine and/or total hip compared with the parent study baseline.

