4.3.8. Visit Windows

Visit windows, which will be used to associate assessments with a scheduled visit, will be used only for summarizing data by visit. The windows for scheduled assessments are shown in [Table 3: Visit Windows for Monthly and Quarterly Assessments \(Monthly and Quarterly Visit, Lab and PGA\) \(Monthly and Quarterly Visit, Lab and PGA\)](#), [Table 4 \(BMD\)](#), [Table 5 \(electrocardiogram \[ECG\]\)](#), [Table 6 \(EHP-30\)](#), [Table 7 \(EHP work domain and EQ-5D-5L\)](#), [Table 8 \(PGIC\)](#), [Table 9 \(Endometriosis Biopsy\)](#), [Table 10 \(Mammogram\)](#), and [Table 11 \(eDairy\)](#) respectively. For safety assessments, the study day will be used to determine the associated visit window. There will be no separation of data from the pivotal phase 3 and extension study. For example, if an assessment in the extension study falls in the Week 24 visit window, it will be summarized as Week 24.

If the results from more than one assessment are within a given visit window, the non-missing result from the assessment closest to the target date will be used. If two assessments are equally close to the target day, the earlier assessment will be used. For summaries of shift from Baseline in safety parameters, all values will be considered for these analyses.

Table 3: Visit Windows for Monthly and Quarterly Assessments (Monthly and Quarterly Visit, Lab and PGA)

Visit	Start Day	Target Day	End Day
Week 4 ^a	1(2 ^b)	29	43
Week 8	44	57	71
Week 12	72	85	99
Week 16	100	113	127
Week 20	128	141	155
Week 24	156	169	183
Week 28	184	197	211
Week 32	212	225	239
Week 36	240	253	267
Week 40	268	281	295
Week 44	296	309	323
Week 48	324	337	351
Week 52	352	365	411
Week 65	412	456	502
Week 78	503	547	593
Week 91	594	638	684
Week 104	685	731	Date of last dose + 6 days
Safety Follow-Up ^c	Date of last dose + 7 days	Date of last dose + 30 days	Date of last dose + 60 days

^a Start day of Week 4 for study day 1 includes only post-Baseline assessments that occurred after the first dose.

^b For Patient Global Assessments (PGAs), the start day of the Week 4 visit window begins at Day 2.

^c The safety Follow-Up visit window will be restricted to assessments prior to the date of initiation of another investigational agent or hormonal therapy affecting the hypothalamic- pituitary- gonadal axis or surgical intervention for endometriosis-associated pain.

Table 4: Visit Windows for Bone Mineral Density Assessments

Visit	Start Day	Target Day	End Day

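### Post-treatment BMD summaries mix loss-triggered and unselected scans, and the recovery percentage has no defined threshold, reference scan or denominator

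*SAP*

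**What the plan says.** The post-treatment part of SAP section 9.3.5 plans three summaries:

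- A count: "All available 6-month and 12-month post-treatment follow-up BMD data will be summarized to display the number and percent of patients" who completed follow-up, "who met the threshold for recovery, and who did not meet the threshold for recovery".
- A table of recovery: "Summary of BMD loss recovery during post treatment follow up will be provided by location and by pivotal phase 3 study treatment group".
- A table of change: "Summaries will be presented of percent change in BMD from baseline for patients who entered post-treatment follow-up period", by site and pivotal treatment group.

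Table 1 lists percent change in BMD from the parent-study baseline at 6 and 12 months post-treatment as a safety endpoint.

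Table 2 sets out who is scanned. Under AM 3.1, a woman who completed the extension had a 6-month scan only if "bone mineral density loss at the lumbar spine (L1-L4) or total hip was > 3%, relative to the pivotal phase 3 study baseline". The 12-month scan was conditional again: "12-Month Post-Treatment DXA: patients have 6-month post-treatment follow-up scans that show bone loss of > 1.5% at the lumbar spine" and/or more than 2.5% at the total hip. AM 4.0 drops the condition: "All ongoing patients, after they complete the Week 104 visit or terminate the study early, will return for a 6-month PTFU DXA" and another at 12 months.

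On later therapy, Table 3 footnote c says: "The safety Follow-Up visit window will be restricted to assessments prior to the date of initiation of another investigational agent or hormonal therapy" acting on the hypothalamic-pituitary-gonadal (HPG) axis. Table 9 has a similar exclusion for biopsies. Table 4, the BMD windows, has none. Section 9.3.5 puts post-treatment concomitant medications in a listing only.

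**The concern.** A recovery percentage needs three things fixed in advance: who had something to recover, from which scan, and by how much. Section 9.3.5 fixes none of them, so two programmers could follow the text and produce very different figures.

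Even with a definition, the pooled scans would mix two kinds of women. Those scanned because the last reading was low will on average read higher next time through measurement error alone. Those scanned regardless of BMD have no such selection. The 12-month scans encouraged under AM 3.1 are selected a second time, for loss that persisted at 6 months. The 6- and 12-month results therefore describe different women.

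At stake is what the report says about reversibility of bone loss. Both the recovery percentage and the mean change would partly reflect which amendment applied to whom, and possibly what hormonal treatment was taken afterwards.

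**Working it through.** The SAP states no recovery figure, so there is nothing to reproduce. The check sets the rules side by side and then illustrates their effect.

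**1. Who is scanned (Table 2)**

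| Version | 6-month scan | 12-month scan |
|---|---|---|
| Original, AM 1.0 | loss > 3% at lumbar spine or total hip | none |
| AM 2.0 | after early termination, loss > 2%, > 3% or > 7% by timing | none |
| AM 3.1 | loss > 2% or > 3%, by timing and most recent scan | encouraged if 6-month loss > 1.5% spine and/or > 2.5% hip |
| AM 4.0 | all ongoing; requested if within 6 months of last treatment | all ongoing; requested if within 12 months |

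The trigger is loss at the spine or the hip, so a triggered woman may have no loss at the other site. A recovery denominator therefore has to be defined site by site.

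**2. What could serve as the recovery threshold**

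Table 2 contains several BMD cut-offs: 1.5% and 2.5% (AM 3.1, 12-month scan) and 3% (AM 4.0, referral and laboratory tests). None is called a recovery threshold. Section 9.2 refers to incomplete recovery without defining it.

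**3. Later therapy**

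| Table | Window from last dose | Cut at new investigational or hormonal therapy |
|---|---|---|
| 3, safety follow-up | +7 to +60 days | yes |
| 9, biopsy | +7 to +60 days | yes |
| 4, BMD 6 months | +150 to +304 days | no |
| 4, BMD 12 months | +305 to +425 days | no |

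**4. Illustration with zero true recovery (all inputs assumed)**

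Let T be the true percent change at end of treatment, with mean -1 and SD 3. Scan error has SD 1.5, and the baseline error B is shared. The last on-treatment reading is E = T - B + e1, and the follow-up reading is F = T - B + e2.

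- Variance of E or F = 9 + 2 × 2.25 = 13.5, so SD = 3.674. Covariance = 9 + 2.25 = 11.25, so correlation = 0.833.
- Share triggered, E < -3: Φ((-3 + 1)/3.674) = Φ(-0.544) = 29.3%.
- Share with no observed loss, E ≥ 0: Φ(-1/3.674) = Φ(-0.272) = 39%.
- All women scanned, F > -3: 1 - 0.293 = 71%.
- Triggered women, F > -3: 27% (simulation of 1,000,000 women).
- Triggered women, mean E: -1 - 3.674 × 1.174 = -5.31. Mean F: -1 - 0.833 × 3.674 × 1.174 = -4.59. Apparent rise: 0.72 points. Here 1.174 = φ(0.544)/Φ(-0.544).

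Pooling triggered women with all-comers (share w triggered):

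| w | Meeting the 3% cut-off | Mean percent change |
|---|---|---|
| 25% | 0.25 × 27 + 0.75 × 71 = 60% | 0.25 × (-4.59) + 0.75 × (-1) = -1.90 |
| 50% | 49% | -2.80 |
| 75% | 38% | -3.69 |

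Across assumed means of -0.5, -1 and -2%, SDs of 2 and 3%, and scan errors of 1, 1.5 and 2%:

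- 3% cut-off: 60-85% of all-comers against 17-43% of triggered women.
- 1.5% cut-off: 42-66% against 3-24%.
- Apparent mean rise in triggered women: 0.3-1.5 points.

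**The case against.** The best defence is that the SAP does not say what a critic might assume.

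- **Women without loss counted as recovered.** A reader might infer this from the phrase about all available data. The SAP does not state it. The phrase also covers the count of women who completed follow-up, and the title of the recovery table presupposes a loss. Nor would a woman without loss meet every possible threshold: one defined as a share of loss regained would not apply to her. What stands is that no loss subset is defined.
- **The data cannot show recovery.** That goes too far. Post-treatment percent change can be set beside on-treatment change by site and group, and AM 4.0 scanning is not conditional on loss.
- **Contamination by hormonal therapy.** Its presence is inferred from a missing exclusion, and the number of such women is unknown. The Table 3 and Table 9 footnotes govern the 30-day follow-up and need not carry over. Including every scan in a long bone-safety follow-up is a legitimate choice. That argues for a flag and a second summary, not for exclusion.
- **Descriptive study; definition may sit in the protocol.** Both are fair. But a descriptive recovery percentage will still be read as reversibility, and the analysis plan should state or cite the definition that its table uses.

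Table 4 and section 9.3.5 do keep the 6- and 12-month results apart. The difficulty is how women enter each.

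**Conclusion.** The point holds in a limited form. As written, the recovery percentage is not interpretable, because its threshold, reference scan and denominator are open. The mean percent change from baseline, which is the actual Table 1 endpoint, is defined but averages over loss-selected and unselected women in an unknown mix.

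In the worked scenario, moving the triggered share from 25% to 75% changes the recovery figure by 22 points (60% to 38%) and the mean change by about 1.8 points (-1.90 to -3.69), with no change in any woman's bone. These sizes rest on assumed distributions and an assumed cut-off; they are not trial estimates. The shares of triggered scans and of women on new therapy are not in the SAP.

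The issue should be corrected before the tables are produced. It does not invalidate the follow-up data.

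**What to change.** In section 9.3.5:

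1. State the recovery threshold, take the last on-treatment scan as the reference, and use as denominator the women with a qualifying loss at that site. Report women without loss separately. The choice of threshold is for the sponsor; the SAP needs one definition, reconciled with the cut-offs in Table 2.
2. Make the AM 4.0 scans not selected by loss the main post-treatment estimate, showing percent change from baseline and from the last on-treatment scan. Put loss-triggered scans in a separate column, and show paired last on-treatment, 6-month and 12-month values. Add a note that improvement in loss-selected women partly reflects regression to the mean. Item 1 does not remove this: in the illustration, 17-43% of triggered women still pass a 3% cut-off with no true recovery.
3. Flag scans on or after the start of another investigational or HPG-axis hormonal therapy, and summarise with and without them.

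The cost is SAP wording, a few more table columns and smaller denominators. DXA results and post-treatment medications are already collected. The SAP does not say whether the amendment in force is recorded for each woman. If it is not, the split by last on-treatment loss can still be made from the DXA data.
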